6.3 Management of Overdose

An overdose dose of BN101/belumosudil has not been established. In clinical studies of BN101/belumosudil, a 500 mg BID dose of BN101/belumosudil given to healthy volunteers for 28 consecutive days was well tolerated, suggesting that the drug has a wide safety window and that overdose is unlikely. There is no known antidote for BN101/belumosudil and no specific treatment recommendations in case of suspected overdose. Investigators should exercise comprehensive judgment in the management of subjects with suspected overdose based on their clinical condition.

[§]The maximum time allowed for suspension of BN101/belumosudil administration due to toxicity was 14 days, and subjects who discontinued for more than 14 days were required to withdraw from the study. If a subject can tolerate 1 full cycle of treatment after a BN101/belumosudil dose reduction, the dose may be restored to the dose prior to the reduction for the next cycle.

The reporting and management of overdose is detailed in Section 8.9.

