Eligible subjects will be enrolled to receive BN101/belumosudil (every 28-day cycle) until cGVHD progression [Evaluated by the investigator based on the National Institutes of Health (NIH) Consensus Development Project on Criteria for Clinical Trials in cGVHD(2014) diagnosis and staging, and response criteria, hereinafter referred to as the NIH Consensus Criteria (2014)], intolerable toxicity, initiation of a new cGVHD therapy, recurrence of hematological neoplasm (according to the recurrence criteria of the corresponding primary hematologic tumor), loss to follow-up, withdrawal of consent, or death, etc., whichever occurred first.

For subjects assessed as "Lack of Response - Mixed" and "Lack of Response - Progression" (See

section 7.1.1, table 4), if the investigator believed that these subjects could continue to benefit from treatment with BN101/belumosudil, the treatment may be continued after a written application was submitted, and approval from the Sponsor's Medical Director as well as documentation of the subject's willingness to continue treatment was obtained. In such cases, the rationale for continuing treatment must be clearly documented. In addition, "Lack of Response - Mixed" will be considered a progression event in the analysis of outcomes.

For subjects who did not achieve any response after 12 cycles of BN101/belumosudil treatment during the main study (the end of the main study is defined in section 3.5 of the main body), they should discontinue the investigational product treatment and withdraw from the study if they were judged by the investigator to have no clinical benefit (e.g., improvements in organ score, improvements in Lee symptom scores, reductions of corticosteroid/tacrolimus doses).

(1) Completion of study drug therapy

- Completion of study drug therapy as defined by the protocol;
- cGVHD disease progression during treatment;
- Death of the subject.

(2) Early termination of study drug therapy

Refers to the situation in which an enrolled subject becomes unfit to continue treatment with the study drug during the course of the study. Early termination of study drug treatment is defined as follows:

- Recurrence of the subject's hematologic tumor during the course of the trial (according to the criteria for recurrence of the corresponding primary hematologic tumor).

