- The subject is discontinued due to an adverse event or serious adverse event that makes continuation of study drug treatment inappropriate; or the subject is discontinued due to an adverse event or serious adverse event for more than 14 days.
- The investigator determines that the subject's continued treatment with the study drug may pose a potential risk greater than benefit to the subject, including: pregnancy; enrollment in the study and discovery that the subject does not meet the study protocol inclusion criteria and that continued treatment with the study drug poses a risk greater than benefit to the subject; failure to follow the protocol or doctor's orders, unauthorized use of other treatments, or failure to take the medication in a timely manner and at a dosage that would interfere with the assessment of efficacy and increase potential safety risks.
- Subject withdraws informed consent/withdraws from the study.
- Subject lost to follow-up.

After discontinuation of study medication, subjects will undergo end-of-treatment visits and enter

a safety follow-up period (including a 28-day follow-up after the last dose and a long-term safety follow-up).

Subjects have the right to withdraw from the study at any stage of the study under the terms of informed consent, or to be "withdrawn" (or "dropped") from the study even if they do not explicitly withdraw from the study but no longer accept the study medication or the study evaluations. The reasons for withdrawal should be understood and documented to the extent possible, e.g., perceived intolerance of certain AEs associated with the study drug, other reasons for not being able to continue in the clinical study, or unexplained loss of visits.

(3) Treatment of withdrawn subjects

The investigator must complete the reason for the subject's withdrawal from the study on the electronic case report form (eCRF) and contact the subject to complete the evaluation program for the end-of-treatment visit (EOT) and safety follow-up (28 ± 7 days after the last dose of study drug or prior to initiation of a new treatment for systemic cGVHD) whenever possible, and keep records, documenting, whenever possible, the time of the subject's last dose of study drug. The eCRF should be retained for subjects who withdraw from the trial for whatever reason.

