4.3.6 Long-Term Safety Follow-Up

Subjects who terminate study treatment early before the end of the main study will be contacted by telephone by the study center approximately every 12 weeks to confirm their survival, any changes in cGVHD treatment, and any antitumor therapy until the end of the main study (see Section 3.5).

Subjects who have not yet experienced cGVHD progression at the end of the study, and in the judgment of the investigator, the benefits of continued dosing outweigh the risks, may submit a written request and, upon approval by the sponsor's Medical Director and documentation of the subject's willingness to continue the treatment, the sponsor will continue to provide BN101/belumosudil medication at no cost until cGVHD progression, intolerable toxicity, initiation of a new cGVHD therapy, recurrence of hematological neoplasm, loss to follow-up, withdrawal of consent, or death, etc., whichever occurred first. During this period, subjects will return to the study center in accordance with their clinical practice, and the study will continue to collect SAEs, study drug use, and survival (or can be contacted by phone). In addition, SAEs for this group of subjects will need to be collected up to 28 days (±7) after the last dose or the initiation of new cGVHD therapy.

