6.1 Dose Adjustment

Subjects who experience any clinically significant toxicity during treatment will need to be considered for suspension or termination of study drug therapy. Subjects who experience an AE related to study treatment may be dosed according to Table 3.

Table 3 BN101/belumosudil dose adjustment

Toxicity*	Dose Adjustment
≥ grade 3 hepatotoxicity (ALT/AST/TBIL)	 Suspend BN101/belumosudil administration; Within 14 days§toxicity does not return to ≤ Grade 1 or baseline level, then discontinue BN101/belumosudil therapy; Within 14 days§toxicity returns to ≤ Grade 1 or Baseline level, resume BN101/belumosudil administration at a reduced dose level [e.g., 200 mg QD → 200 mg once every other day (QOD)]; If the reduced dose level is administered for one full treatment cycle tolerated by the subject without recurrence of Grade 1 or greater hepatic function abnormality, return the dose to the original level for the following treatment cycle[e.g., 200 mg QOD → 200 mg QD]; If this toxic reaction recurs after the reduced dose level, terminate BN101/belumosudil treatment.
Other ≥ grade 3 clinically significant toxicity associated with BN101/belumosudil	 Suspend BN101/belumosudil administration; Within 14 days§toxicity does not return to ≤ Grade 1 or baseline level, then discontinue BN101/belumosudil therapy; Within 14 days§toxicity returns to ≤ Grade 1 or baseline level, then BN101/belumosudil administration is resumed at a reduced dose level [e.g., 200 mg QD → 200 mg QOD]; if the reduced dose level is administered for a full treatment cycle as tolerated by the subject, and there is no recurrence of Grade 1 or higher of this abnormality, then the next cycle of treatment the dose will be restored to the original level [e.g., 200 mg QOD → 200 mg QD]; If the toxic reaction recurs after administration at a reduced dose level, BN101/belumosudil treatment will be discontinued.

^{*} Severity of toxicity was determined according to NCI CTCAE v5.0.

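### The Table 3 footnote withdraws patients from the study after a toxicity suspension of more than 14 days, while Sections 3.3 and 4.3.6 keep the same patients in long-term follow-up

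*Protocol*

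**What the plan says.** The protocol describes one event, a suspension for toxicity lasting more than 14 days, in several places.

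- **Table 3 footnote (Section 6.1; also under the dose table in the synopsis):** "subjects who discontinued for more than 14 days were required to withdraw from the study". In the extracted text the footnote is printed under Section 6.3, but its § mark ties it to Table 3.
- **Table 3 body:** if within 14 days "toxicity does not return to ≤ Grade 1 or baseline level, then discontinue BN101/belumosudil therapy". This stops the drug and says nothing about leaving the study.
- **Section 3.3(2):** lists among the forms of early termination of study drug that "the subject is discontinued due to an adverse event or serious adverse event for more than 14 days". It then says: "After discontinuation of study medication, subjects will undergo end-of-treatment visits and enter" a safety follow-up period, described as "including a 28-day follow-up after the last dose and a long-term safety" follow-up. The synopsis has the same list and the same consequence.
- **Section 4.3.6:** "Subjects who terminate study treatment early before the end of the main study will be contacted by telephone by the study center" about every 12 weeks, to ask about survival, changes in cGVHD treatment and antitumour therapy. Appendix 1 note 17 repeats this for anyone who stops study therapy during the main study.
- **Section 3.3(3), on withdrawn subjects:** the investigator is to "contact the subject to complete the evaluation program for the end-of-treatment visit (EOT) and safety follow-up" where possible. The long-term calls are not mentioned there.

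SAP Section 5.1.2 censors FFS and TTNT at the later of the last response assessment and the last long-term follow-up contact, where available. SAP Table 2 does the same for the tertiary definition of duration of response. No censoring rule is stated for overall survival (OS).

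**The concern.** The protocol gives the same patient two follow-up statuses. Under Sections 3.3 and 4.3.6 the patient stops drug and stays under observation. Under the footnote the patient leaves the study, and the paragraph on withdrawn subjects names only the end-of-treatment and 28-day visits.

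FFS, TTNT and OS all need information from after the drug is stopped. A patient taken off treatment for toxicity that has not resolved may well need another systemic cGVHD therapy, which is an FFS event and the TTNT event. If such patients go out of view when they stop drug, the censoring may be related to the outcome. The Kaplan-Meier curve would then describe the patients who tolerated the drug better than it describes all those treated.

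**Working it through.** No sample size, power or other figure in the plan depends on this point, so there is nothing to reproduce. The check has three parts.

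**1. The passages side by side**

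| Place | What the patient leaves | Follow-up named |
|---|---|---|
| Table 3 body | Drug | None stated |
| Table 3 footnote and synopsis copy | Study | None stated |
| Section 3.3(2) and synopsis copy | Drug | End-of-treatment visit, 28-day visit, long-term |
| Section 3.3(3), withdrawn subjects | Study | End-of-treatment visit, 28-day visit |
| Section 4.3.6, Appendix 1 note 17 | Drug | Calls about every 12 weeks |

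Table 3 disagrees with its own footnote, and the synopsis disagrees with itself.

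**2. What is lost if the footnote is applied literally**

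- Appendix 1 collects other cGVHD therapies only until 28 days after the last dose. After that, the calls are the only scheduled source for new cGVHD therapy, antitumour therapy and survival.
- The end-of-treatment visit includes a response assessment. The 28-day visit (Section 4.3.5) does not. Without calls, the SAP rule therefore censors FFS and TTNT at the last response assessment, around the end-of-treatment visit.
- The calls include no response assessment, so whether they take place hardly bears on ORR, which is best response at any post-baseline assessment.

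**3. Illustration of size**

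Taken from the protocol: N = 30 (Section 10.2) and median FFS of 10.7 months in KD025-208 (Section 1.4.2).

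Assumed, with no source in the documents: exponential FFS; k patients censored at month 3; a hazard after withdrawal that is HR times that of the others, with the extreme that all of them fail by month 12.

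- Rate: ln 2 / 10.7 = 0.0648 per month. S(3) = 0.823, S(9) = 0.558, S(12) = 0.460.
- Share of patients event-free at month 3 who are then lost: f = k / (30 × S(3)).
- Kaplan-Meier value with these patients censored: S(3) × S(9) = 0.460.
- Value with full follow-up: S(3) × [(1 − f) × S(9) + f × S(9)^HR].

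For k = 3 and HR = 2: f = 3 / 24.70 = 0.121. The full follow-up value is 0.823 × [0.879 × 0.558 + 0.121 × 0.312] = 0.435, so the overstatement is 46.0 − 43.5 = 2.5 points.

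Overstatement of 12-month FFS, in percentage points:

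| Patients lost | HR 1 | HR 2 | HR 3 | All fail |
|---|---|---|---|---|
| 1 of 30 | 0 | 0.8 | 1.3 | 1.9 |
| 3 of 30 | 0 | 2.5 | 3.8 | 5.6 |
| 6 of 30 | 0 | 4.9 | 7.7 | 11.2 |

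For scale, the approximate 95% half-width of a 46% proportion at n = 30 is 1.96 × √(0.46 × 0.54 / 30) = 17.8 points.

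At an assumed 5% rate of such suspensions, the chance of at least one among 30 patients is 1 − 0.95^30 = 78.5%. At an assumed 10% it is 95.8%.

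**The case against.** The strongest answer is that the follow-up rules already cover these patients. Section 3.3(2) lists withdrawal from the study itself among the forms of early drug termination, and then sends subjects who stop the drug on to long-term follow-up. Section 4.3.6 and Appendix 1 note 17 make no exception for withdrawn subjects. Section 3.3(3) does not say that its two visits are the only ones.

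The protocol also uses study withdrawal loosely. Section 8.9 withdraws pregnant subjects but continues to follow them. Sections 3.5 and 4.1 describe a taper for subjects withdrawing from the study, where SAP Section 4 speaks of discontinuing study treatment. On this reading the footnote means no more than coming off drug.

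Much of this stands. Continued follow-up is the better-supported reading, and the loss of data is a risk, not the plan. It does not remove the conflict. Table 3 uses two different terms for one event, and Section 10.6.3 summarises adverse events leading to study withdrawal separately from those leading to treatment discontinuation, so the distinction carries meaning elsewhere. A site that works from the dose table could reasonably stop calling.

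A reader might also infer more than the documents support:

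- **That the 12-cycle rule for non-responders adds to the bias.** Section 3.3 says of those judged to have no clinical benefit that "they should discontinue the investigational product treatment and withdraw from the study". Twelve cycles are 12 × 28 = 336 days, so these patients have been observed almost to the last SAP landmark of 12 months. The rule barely touches that figure.
- **That censoring would fall at the 28-day visit.** The SAP uses response assessments and long-term contacts, and the 28-day visit is neither.
- **That a definite bias can be quoted.** The number affected and their later prognosis appear nowhere in the documents.

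**Conclusion.** The inconsistency is real and should be reconciled. It creates a risk of informative, favourable censoring of FFS and TTNT if sites apply the footnote literally. OS is exposed in the same way, although without a stated censoring rule its censoring date cannot be given.

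The size is unknown. It is zero if sites follow Sections 3.3 and 4.3.6, and zero if prognosis after withdrawal matches that of the other patients. It is a few points on 12-month FFS (2.5 to 5.6 in the illustration) if about 3 of 30 patients are lost and do worse. That range rests on the assumed number, timing, hazard ratios and exponential curve, and it is well inside the sampling error at n = 30.

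The affected endpoints are secondary and descriptive, and no hypothesis is tested. The documents do not support reading this as a threat to the primary endpoint: ORR is little affected. The case for acting is that the change is cheap and protects the only scheduled source of late post-treatment data.

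**What to change.** Reconcile the Table 3 footnote and its synopsis copy with Sections 3.3 and 4.3.6, so that stopping study drug and leaving the study are distinguished. State once, and refer to it from the other places, that subjects who stop drug remain in the existing long-term follow-up unless they withdraw consent. Word Section 3.3(3) to agree.

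The 14-day rule itself is a clinical matter on which this point takes no view; only the follow-up status after it needs to be stated consistently.

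The cost is a wording amendment and a note to sites. The calls are already in the protocol, so no visit or procedure is added.

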6.4 Combinations of medications and treatments

All comorbid medications and treatments during the study period are to be documented. If a new systemic cGVHD treatment is initiated during the study period it will be considered as initiation of a new cGVHD treatment and will be considered as a failure of BN101/belumosudil treatment.

6.4.1 Corticosteroids

Therapeutic doses of corticosteroids are to be collected throughout the study. After ≥2 weeks of BN101/belumosudil use, the dose of corticosteroids may be reduced at the discretion of the investigator.

A transient increase in corticosteroid dose (no more than 1 mg/kg/day prednisone equivalent) is permitted during cGVHD episodes, but this dose must be adjusted to the pre-enrollment dose level within 6 weeks. If the dose remains elevated for more than 6 weeks, it will be considered a BN101/belumosudil treatment failure. The occurrence of more than 2 episodes of cGVHD requiring an increase in corticosteroid dose during the first 6 months of BN101/belumosudil treatment will also be considered a BN101/belumosudil treatment failure.

If the planned response assessment falls during a cGVHD episode of treatment, this response assessment will still be performed as planned, but the assessment will not be included in the primary efficacy analysis.

6.4.2 Systemic cGVHD Therapies

Per the eligibility criteria, subjects receiving standard of care systemic cGVHD therapies such as calcineurin inhibitors (tacrolimus, cyclosporine), sirolimus, MMF, methotrexate, rituximab or ECP, may be enrolled if they have been on a stable dose/schedule. During the study treatment period, it is permissible to continue cGVHD treatment as described above at doses/regimens that have stabilized prior to enrollment, but it is not permissible to increase the dosage of these medications unless the increase in dosage is used only to maintain the current therapeutic level of the medication (e.g., to maintain the current blood concentration). Doses and schedules of these therapies will be collected throughout the study and changes will be documented.

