All comorbid medications or treatments will be documented during the study period. Initiation of new systemic cGVHD treatment will be considered as starting a new cGVHD treatment and will be considered a failure of BN101/belumosudil treatment.

- Transient increases in corticosteroid dose (no more than 1 mg/kg/day of prednisone equivalent) for treatment of cGVHD episodes will be permitted during the study treatment period, provided that the dose is reduced to pre-enrollment levels within 6 weeks. If the dose remained elevated for more than 6 weeks, it was considered a BN101/belumosudil treatment failure. More than 2 episodes of cGVHD requiring an increase in the dose of corticosteroid therapy within the first 6 months of BN101/belumosudil treatment will also be considered a BN101/belumosudil treatment failure.
- Continuation of treatment with calcineurin phosphatase inhibitors (e.g., tacrolimus, cyclosporine), sirolimus, MMF, methotrexate, azathioprine, or extracorporeal photochemistry (ECP), which have been stabilized at baseline, is permitted during study treatment.
 - Local/organ-specific therapy for cGVHD is allowed during study treatment.
- During study treatment, CYP3A4 inducers (e.g., rifampin, phenobarbital) are prohibited, proton pump inhibitors (e.g., rabeprazole, omeprazole) are permitted for short

Concomitant medication and concomitant therapy

	periods of time only (no more than 1 week), and CYP1A2 inhibitors/inducers, CYP3A4
	inhibitors, drugs that prolong the QT/QTc interval should be used with caution (see Appendix for details of CYP3A4 and CYP1A2 inhibitors/inducers, and drugs that prolong the QT/QTc
	interval).
	- The use of other systemic therapies for cGVHD (including rituximab, ruxolitinib,
	ibrutinib, etc.) or other clinical trial medications is prohibited during study treatment.
	- Tobacco, alcohol, and caffeinated beverages or foods are prohibited on the day of PK sample collection.
	The primary efficacy endpoint was the Overall Response Rate (ORR, including
	Complete Response [CR] and Partial Response [PR]), assessed according to the NIH consensus criteria (2014).
Efficacy endpoints	Secondary efficacy endpoints included median Duration of Response (DOR), Change in Lee Symptom Scale Score, Response rate by organ system, Percentage of subjects with best efficacy as PR and percentage of subjects with best efficacy as CR, Change in

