3.2 Exclusion Criteria

Subjects who met any of the following conditions would be excluded from the study:

(1) Received a systemic investigational cGVHD treatment within 28 days of study entry, but prior treatment is allowed with a washout of at least 28 days or 5 half-lives.[Note: Corticosteroids, CNIs, sirolimus, mycophenolate mofetil (MMF), methotrexate, azathioprine, and *in vitro* photochemotherapy (ECP) are acceptable and subjects must have been on a stable dose/regimen of these for at least 2 weeks prior to screening].

- (2) Recurrence of hematologic tumor (according to criteria for recurrence of the corresponding primary hematologic tumor) or post-transplant lymphoproliferative disease at screening.
- (3) Current treatment with ibrutinib (except for ibrutinib with a washout of at least 28 days prior to the first dose of the investigational product).

Laboratory Tests

- (4) Absolute neutrophil count (ANC) $< 1.5 \times 10^9$ /L.
- (5) Platelet count $< 50 \times 10^9/L$.
- (6) Alanine aminotransferase (ALT) $> 3 \times \text{upper limit of normal (ULN)}$, aspartate aminotransferase (AST) $> 3 \times \text{ULN}$
- (7) Total bilirubin (TBIL) $> 1.5 \times ULN$.
- (8) Creatinine clearance (CrCl) < 60 mL/min (Cockcroft-Gault formula).

General Criteria

- (9) Pregnant or lactating women.
- (10) History of severe illness, or other evidence of severe illness, or any other conditions that would make the subject, in the opinion of the investigator, unsuitable for the study
- History of severe [New York Heart Association (NYHA) functional class III or IV] cardiovascular disorder, including but not limited to ventricular arrhythmias requiring clinical intervention, uncontrolled hypertension (systolic blood pressure ≥ 160 mmHg and/or diastolic blood pressure ≥ 100 mmHg); unstable angina pectoris, acute coronary syndrome, congestive cardiac failure, stroke, or other ≥ Grade 3 cardiac events within 6 months prior to enrollment; and NYHA functional class ≥ II or left ventricular ejection fraction (LVEF) < 50% by cardiac ultrasound at screening.

- Inability to take oral medications, severe (NCI CTCAE v5.0≥ Grade 3) chronic gastrointestinal dysfunction, malabsorption syndrome, or any other condition that affects gastrointestinal absorption.

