6.4.8 Other Prohibited Combination Medications

The use of systemic immunosuppressive drugs against cGVHD (including rituximab, ruxolitinib, ibrutinib, etc.) or other clinical trial medications is prohibited during study treatment.

Tobacco, alcohol, and caffeinated beverages or foods are prohibited on the day of PK sample collection.

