10.3 Statistical Analysis Population

Modified Intent to Treat (mITT): all subjects enrolled and having used at least one dose of study drug.

Per Protocol Set (PPS): The PPS was a subset of the mITT, and included all subjects who have used the study drug after enrollment and have had at least 1 post-treatment efficacy assessment, as well as no major protocol deviations. The exact definition of a major protocol deviation and the inclusion criteria for the PPS were finally determined in the data review meeting.

Safety Set (SS): All subjects who had used the study drug after enrollment and had at least 1 safety assessment.

Pharmacokinetic analysis Set (PKS): all subjects who have used the study drug since enrollment and have post-administration PK data.

Demographic and baseline characteristics of subjects were statistically analyzed based on mITT. mITT was the primary analysis population for the primary efficacy endpoint and PPS was the secondary analysis population. Safety analysis based on SS and PK analysis based on PKS.

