5.4. Protocol Deviation

All protocol deviations will be identified and classified as major or minor (as defined below) before the clinical database lock.

Major Deviations: Protocol deviation that may impact the accuracy, and/or reliability of the study data or that may impact patient rights, safety or well-being.

Minor Deviations: Protocol deviation that does not impact the accuracy, and/or reliability of the study data or patient rights, safety or well-being.

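### Rituximab is both permitted (Protocol 6.4.2) and prohibited (Protocol 6.4.8 and synopsis) during study treatment, so a subject who continues it has no single protocol status

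*Protocol*

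**What the plan says.** **Permission.** Protocol 6.4.2, citing the eligibility criteria, ends its list of standard systemic cGVHD therapies with "methotrexate, rituximab or ECP, may be enrolled if they have been on a stable dose/schedule". It then adds: "During the study treatment period, it is permissible to continue cGVHD treatment as described above at doses/regimens that have stabilized prior to enrollment". Rituximab is one of the therapies so described.

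**Prohibition.** Protocol 6.4.8 states: "The use of systemic immunosuppressive drugs against cGVHD (including rituximab, ruxolitinib, ibrutinib, etc.) or other clinical trial medications is prohibited during study treatment". The synopsis, under concomitant medication, has a matching prohibition that begins "The use of other systemic therapies for cGVHD (including rituximab, ruxolitinib". Neither text exempts use that was stable before enrolment.

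**Eligibility.** No inclusion or exclusion criterion names rituximab. The note to exclusion criterion 1 (Protocol 3.2) lists acceptable stable therapies as "Corticosteroids, CNIs, sirolimus, mycophenolate mofetil (MMF), methotrexate, azathioprine" and ECP.

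**Deviations and analysis sets.** SAP 5.4 says: "All protocol deviations will be identified and classified as major or minor (as defined below) before the clinical database lock". SAP 8.3.2 gives taking an excluded medication as an example of a major-deviation type. SAP section 7 keeps subjects with major deviations out of the PPS. On the details, Protocol 10.3 says: "The exact definition of a major protocol deviation and the inclusion criteria for the PPS were finally determined in the data review meeting".

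**The concern.** The conflict is confined to one case: a subject on stable rituximab at enrolment who continues it during treatment. A subject who receives no rituximab on study breaches neither rule.

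In that one case three things depend on which section is read.

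- **Conduct.** Protocol 3.3 lists grounds on which the investigator may end study drug early after judging that risk exceeds benefit. They include "unauthorized use of other treatments, or failure to take the medication in a timely manner". Whether continued rituximab counts as unauthorized has no single answer in the text.
- **Deviation tables.** The same use is either compliant or a candidate excluded-medication deviation.
- **PPS membership.** If the use is classed as a major deviation, the subject leaves the set used for the sensitivity analysis of the primary endpoint.

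The synopsis plans about 6 to 9 centers, so different sites could read the protocol differently.

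**Working it through.** **Step 1: compare every passage that lists permitted or prohibited systemic cGVHD therapy.**

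| Place | Role of the passage | Rituximab |
|---|---|---|
| Protocol 6.4.2 | May enrol on, and continue, if stable | Named as permitted |
| Protocol 6.4.8 | Prohibited during study treatment | Named as prohibited |
| Synopsis, prohibited therapies | Prohibited during study treatment | Named as prohibited |
| Synopsis, therapies that may continue | Permitted if stable at baseline | Absent |
| Protocol 3.2, exclusion 1 note | Acceptable if stable | Absent |
| Protocol 4.1 | Examples of permitted therapies | Absent |
| SAP section 4 | Examples of permitted therapies | Absent |

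The first three rows contradict one another directly. The last four do not settle the matter. Two of them are open example lists, and exclusion 1 itself concerns investigational cGVHD treatment. Section 6.4.2 relies on the eligibility criteria, but those criteria do not mention the drug.

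**Step 2: effect on the primary analysis.** The mITT set is every enrolled subject who took at least one dose (Protocol 10.3, SAP section 7). Deviation status does not enter that definition, so reclassifying this case moves mITT ORR by 0 points.

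**Step 3: bound on the PPS analysis.** The inputs are N = 30 planned subjects (Protocol 10.2), R responders, k subjects removed from the PPS for this reason alone, and j responders among those k. Assume no other PPS exclusions.

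PPS ORR − mITT ORR = (R − j)/(30 − k) − R/30 = (kR − 30j) / [30(30 − k)]

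- Largest positive value: j = 0 and R = 30 − k, which gives k/30.
- Largest negative value: j = k and R = k, which gives −k/30.

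The difference therefore cannot exceed k/30 in absolute value: 1/30 = 3.3 points, 2/30 = 6.7 points, 3/30 = 10.0 points.

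**Step 4: a less extreme illustration.** Take R = 22, from the 200 mg QD ORR of 72.7% reported for KD025-213 in Protocol 1.4.2 (0.727 × 30 = 21.8). That trial required at least two prior lines of therapy, so this is only an assumption. mITT ORR is then 22/30 = 73.3%, with exact 95% CI 54.1% to 87.7%.

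| k | Lowest PPS ORR (all removed are responders) | Highest PPS ORR (none are) | Difference from mITT (points) |
|---|---|---|---|
| 1 | 21/29 = 72.4% | 22/29 = 75.9% | −0.9 to +2.5 |
| 2 | 20/28 = 71.4% | 22/28 = 78.6% | −1.9 to +5.2 |
| 3 | 19/27 = 70.4% | 22/27 = 81.5% | −3.0 to +8.1 |

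All of these lie inside the confidence interval for 22/30.

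**The case against.** **The prohibition must already be read narrowly.** Taken literally, the class named in 6.4.8 would also cover calcineurin inhibitors, sirolimus and MMF, which the protocol plainly allows to continue. The synopsis speaks of other systemic therapies, after its bullet on permitted ones, and Protocol 4.1 and 6.4 are concerned with starting new therapy. So 6.4.8 might be taken as subject to the background-therapy rule. That reading works for drugs the prohibition does not name. It does not work for rituximab, which both prohibitions name and which the synopsis list of therapies that may continue omits. Both prohibitions also cover use, not only initiation.

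**Existing procedures would catch it.** Eligibility is confirmed by the sponsor's medical director or the CRO medical monitor before dosing (Protocol 4.3.1). The medical monitor is consulted on unforeseen deviations (11.7), and a data review meeting settles the PPS criteria (10.3). These steps reduce uneven handling, but the people taking them would be applying the same two conflicting rules.

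**The consequences are limited.** This stands. Early termination needs an adverse risk-benefit judgement, not just a label. Taking an excluded medication is only an example of a deviation type and is not automatically major. The PPS is a sensitivity analysis in a descriptive study with no hypothesis test, and k/30 is reached only at extreme response patterns.

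**Conclusion.** The contradiction is real and the current text does not resolve it: the protocol gives continued stable rituximab two incompatible statuses. The main effect is on conduct and deviation coding. The analytic effect is small: none on mITT ORR from deviation status, and at most k/30 on PPS ORR. That bound assumes 30 treated subjects and no other PPS exclusions. Both k and the illustrative 22 responders are assumptions. If no subject continues rituximab on study, nothing in the results changes. The point should be corrected because an operative conduct rule needs one meaning, but it does not threaten the primary result.

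**What to change.** Reconcile Protocol 6.4.2, 6.4.8 and the synopsis, and the exclusion 1 note if needed, so that rituximab has one status throughout. Which status it should have is a clinical decision for the sponsor, and this review takes no position on it.

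Before database lock, record in the deviation classification whether rituximab continued from before enrolment is permitted background therapy or an excluded-medication deviation and, if a deviation, whether it removes the subject from the PPS.

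The cost is one written clarification or amendment, with ethics committee approval if it is judged substantial (Protocol 11.6), and one entry in a classification that SAP 5.4 already requires. Doses and schedules of these therapies are already collected (Protocol 6.4.2, Appendix 1), so no new data or additional analysis is needed.
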